### **2.2.3. Additional Estimand(s)**

There is no defined estimand for other endpoints, and they will be analyzed using Pfizer data standards as applicable.

## **2.3. Study Design**

This is a phase 2b, randomized, double blind, vehicle controlled, parallel group, multicenter study to assess the efficacy, safety and tolerability, and PK of multiple doses of PF-07038124 ointment versus vehicle in treatment of participants, 12 years and older, and with AD or PsO.

In this study, a total of approximately 240 participants with AD or PsO will be randomly assigned to study intervention (PF-07308124 or vehicle).

**Figure 1 Study Design Schema**

### 3. ENDPOINTS AND BASELINE VARIABLES: DEFINITIONS AND CONVENTIONS

#### 3.1. Primary Endpoint(s)

- Proportion of participants achieving IGA score of clear (0) or almost clear (1) (on a 5-point scale) and a reduction from baseline of  $\geq 2$  points at Week 12.

- Proportion of participants achieving PGA score of clear (0) or almost clear (1) (on a 5-point scale) and a reduction from baseline of  $\geq 2$  points at Week 12.

### 3.2. Secondary Endpoint(s)

#### For AD:

- Proportion of participants achieving EASI-75 (75% improvement from baseline) at all study visit time points specified in the SoA.
- Proportion of participants achieving IGA score of clear (0) or almost clear (1) (on a 5-point scale) and a reduction from baseline of  $\geq 2$  points at all study visit time points specified in the SoA, except at Week 12.
- Percent CFB in EASI total score at all study visit time points specified in the SoA.
- Proportion of participants achieving IGA score of clear (0) or almost clear (1) at all study visit time points specified in the SoA.
- Proportion of participants having  $\geq 4$  points of reduction from baseline in weekly averages of PP-NRS at study visit time points specified in the SoA.
- Percent CFB in affected BSA at all study visit time points specified in the SoA.
- Incidence of treatment emergent AEs and SAEs, clinically significant changes in vital signs, ECG, and laboratory tests.
- Incidence of increase in local tolerability severity grades at times indicated in the SoA.

#### For Psoriasis:

[figure not shown]
- Proportion of participants achieving PASI-75 (75% improvement from baseline) at times indicated in the SoA.

- Proportion of participants achieving PGA score of clear (0) or almost clear (1) (on a 5-point scale) and a reduction from baseline of  $\geq 2$  points at times indicated in the SoA, except at Week 12.
- Change from baseline in PASI at times indicated in the SoA.
- Proportion of participants achieving PGA score of clear (0) or almost clear (1) at all study visit time points specified in the SoA.
- Proportion of **adult** participants (18-75 years old) having  $\geq 4$  points of reduction from baseline in weekly averages of PP-NRS at study visit time points specified in the SoA.
- Percent CFB in affected BSA at all study visit time points specified in the SoA.
- Incidence of treatment emergent AEs and SAEs, clinically significant changes in vital signs, ECG, and laboratory tests.
- Incidence of increase in local tolerability severity grades at times indicated in the SoA.

[figure not shown]
### 3.3. Tertiary/Exploratory Endpoint(s)

For AD:

[figure not shown]
CCI

CCI

CCI

### **3.4. Baseline Variables**

In general, for all analyses, baseline will be defined based on observations collected prior to first dose. Baseline values for demographics and height will be based on measures collected at Visit 1/Screening visit. Study Day 1 is defined as the day the participant receives first dose of study drug. For purposes of all other analyses including analyses for change from baseline, the baseline value will be defined as the last measurement before first dose on Day 1. If a value is missing on Day 1, then the last available observation before Day 1 will be

used. For the PP-NRS score, baseline will be defined as the average of all values recorded between Day -7 and Day -1.

### **3.5. Safety Endpoints**

Safety will be assessed by reporting of AEs, ECG, vital signs, local skin tolerability, and clinical laboratory results in all participants who receive at least one dose of the investigational product. Unscheduled safety assessments may be performed at any time during the study to assess any perceived safety concerns. Endpoints will be assessed as:

- Incidence of treatment emergent adverse events.
- Incidence of SAEs and AEs leading to discontinuation.
- Incidence of clinical abnormalities in clinical laboratory values, ECG measurements, and vital signs.
- Change from baseline in ECG measurements and vital signs.
- Incidence of skin tolerability

The safety endpoints will be defined in accordance with Clinical Data Interchange Standards Consortium (CDISC) and Pfizer Standards (CaPS).

#### **3.5.1. Adverse Events**

All adverse events that start on or after the first dosing date and time, if collected, but before the last dose plus the lag time (35 days) will be flagged as TEAEs. The algorithm will not consider any events that started prior to the first dose date. Missing AE start date and time components will be imputed conservatively as the earliest date and time possible.

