### 2.2.1. Clinical Overview

To date, clinical experience with PF-07038124 ointment comprises 3 studies:

1. A Phase 1, multiple ascending dose study in adult healthy participants (C3941001, completed). CCI  

2. A Phase 2a randomized, double-blind study in participants with mild-to-moderate AD or PsO, treated with 0.01% PF-07038124 ointment or vehicle ointment QD for 6 weeks (C3941002, completed). The total duration of study participation was approximately 17 weeks, including a screening period of up to 6 weeks, a double-blind, vehicle-controlled treatment period of 6 weeks, and a safety follow-up period of 4-5 weeks from last dose of study drug to last study visit.

In this study, there were no deaths or SAEs. All treatment-related (all-causality and treatment-related) severe AEs (4 participants) occurred in the vehicle group. There were no treatment-related AEs in the 0.01% PF-07038124 ointment group. The number of TEAEs (all-causality) and participants reporting TEAEs were higher in the vehicle group (15 [29.4%] participants with 26 events) compared to the PF-07038124 group (12 [22.6%] participants with 16 events).

The most common all-causality TEAEs by SOC in the 0.01% PF-07038124 ointment groups was Infections and Infestations (11.3%), and in vehicle group was Skin and Subcutaneous Tissue Disorders (13.7%). There were no participants with application site pain or other skin reaction at application site in the 0.01% PF-07038124 ointment groups.

There were 3 (5.9%) participants in the vehicle group with 3 TEAEs related to COVID-19, and 1 (2.0%) participant had a temporary discontinuation due to COVID-19. No participants in the 0.01% PF-07038124 ointment groups experienced AE related to COVID-19.

The study met the statistical significance for the primary endpoint for both indications.

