### **8.3.1. Time Period and Frequency for Collecting AE and SAE Information**

The time period for actively eliciting and collecting AEs and SAEs (“active collection period”) for each participant begins from the time the participant provides informed consent/assent, which is obtained before the participant’s participation in the study (ie, before undergoing any study-related procedure and/or receiving study intervention), through and including a minimum of 28 calendar days after the last administration of the study intervention.

Follow-up by the investigator continues throughout and after the active collection period and until the AE or SAE or its sequelae resolve or stabilize at a level acceptable to the investigator.

For participants who are screen failures, the active collection period ends when screen failure status is determined.

If the participant withdraws from the study and also withdraws consent for the collection of future information, the active collection period ends when consent is withdrawn.

If a participant permanently discontinues or temporarily discontinues study intervention because of an AE or SAE, the AE or SAE must be recorded on the CRF and the SAE reported using the CT SAE Report Form.

Investigators are not obligated to actively seek information on AEs or SAEs after the participant has concluded study participation. However, if the investigator learns of any SAE, including a death, at any time after a participant has completed the study, and he/she considers the event to be reasonably related to the study intervention, the investigator must promptly report the SAE to Pfizer using the CT SAE Report Form.

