### 5.1. Hypotheses and Decision Rules

Statistical inference will be made on the primary endpoints: IGA/PGA success rate at Week 12. The null hypothesis is that there is no difference between any PF-07038124 doses being tested and vehicle. The alternative hypothesis is that at least one PF-07038124 dose being tested is superior to vehicle with a higher IGA/PGA success rate. The study will be considered positive for each indication when the corresponding null hypothesis is rejected. For each indication, the overall family wise Type I error rate will be controlled at 1-sided 0.025 level using the Hochberg step up procedure.

A sufficient number of AD participants will be screened to achieve approximately 120 participants randomly assigned to study intervention. The sample size calculation is based on the primary efficacy estimand IGA success at Week 12. Assuming 15% IGA success rate for the vehicle arm, a sample size of 40 per arm will have 89% power to detect a treatment difference of 35% under a 1-sided type 1 error 0.0125 for each of the 2 dose levels comparison to vehicle by the unconditional exact test, with an overall Type 1 error 0.025 1-sided. In addition, this sample size will provide 96% power to detect a 42% difference in EASI-75 between an active arm (62% EASI-75) and vehicle (20% EASI-75).

A sufficient number of PsO participants will be screened to achieve approximately 120 participants randomly assigned to study intervention. The sample size calculation is based on the primary efficacy estimand PGA success at Week 12. Assuming 8% PGA success rate for the vehicle arm, a sample size of 30 per arm will have 92% power to detect a treatment difference of 42% under a 1-sided type 1 error 0.008 for each of the three dose levels comparison to vehicle by the unconditional exact test, with an overall Type 1 error 0.025 1-sided. In addition, this sample size will provide 96% power to detect a 44% difference in PASI-75 between an active arm (50% PASI-75) and vehicle (6% PASI-75).

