### **6.7. Safety Summaries and Analyses**

The analysis population for safety is described in [Section 4](#). Safety and tolerability will be assessed by clinical review of all relevant parameters including adverse experiences (AEs), ECG, vital signs, local skin tolerability and laboratory tests. A complete list of laboratory parameters can be obtained in Appendix 2 of the protocol.

All the tables, listings and graphs for adverse events, lab parameters and vital sign and ECG will follow CaPS.

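### SAP 3.5.1 imputes missing AE start components to the earliest possible value with no floor at first dose, so an ambiguous partial date near first dose drops out of the TEAE summaries

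*SAP*

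**What the plan says.** SAP 3.5.1 (Adverse Events) makes three statements that act together.

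1. The inclusion rule covers "All adverse events that start on or after the first dosing date and time, if collected", up to an upper bound set by last dose plus a 35-day lag.
2. The exclusion rule: "The algorithm will not consider any events that started prior to the first dose date".
3. The imputation rule: "Missing AE start date and time components will be imputed conservatively as the earliest date and time possible".

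Protocol 8.3.1 says that active AE collection "begins from the time the participant provides informed consent/assent". Screening may run up to 28 days before Day 1 (Protocol 1.3.1 and 1.3.2), so the AE data can contain true pre-dose onsets.

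Two general references could bear on the rule. SAP 3.5 states: "The safety endpoints will be defined in accordance with Clinical Data Interchange Standards Consortium (CDISC) and Pfizer Standards (CaPS". SAP 6.7 states: "All the tables, listings and graphs for adverse events, lab parameters and vital sign and ECG will follow CaPS". Neither gives a date-imputation rule, and no other section of either document does.

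**The concern.** The earliest-date rule and the exclusion rule work against each other around first dose. Whenever the known parts of a start date allow onset before dosing, the earliest possible date is a pre-dose date, and the exclusion rule then removes the event. For a treatment-emergent flag, the cautious treatment of an ambiguous event is to keep it in. The text describes its rule as conservative, but at this boundary it takes events out.

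TEAE incidence is a listed secondary safety endpoint in both indications (SAP 3.2), and this rule decides which AEs count towards it. Arms have about 30 (PsO) or 40 (AD) participants, so event counts are low and the rule should be unambiguous before the tables are produced.

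A second, conditional point concerns clock times. SAP 3.5.1 compares date and time where time is collected, but its exclusion sentence compares dates only. For a Day 1 AE with a missing time the two sentences can give different answers.

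**Working it through.** The plan gives no figure for this rule, so there is nothing to reproduce. The check applies the text literally and then sizes the result under stated assumptions.

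**Literal application.** Take a first dose on 15 March 2023 at 10:00 (illustrative).

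| Recorded AE start | Imputed start | TEAE as written | With a floor at first dose |
|---|---|---|---|
| March 2023, day missing | 1 March, 00:00 | No | Yes |
| 2023 only | 1 January, 00:00 | No | Yes |
| 15 March, time missing | 15 March, 00:00 | No by date and time; not excluded by date alone | Yes |
| April 2023, day missing | 1 April, 00:00 | Yes | Yes |

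For an AE with the day missing in the month of first dose, the rule excludes it for every first-dose date except the 1st of a month: 365 - 12 = 353 of 365 dates (96.7%). Reading the earliest possible date as no earlier than a consent date 28 days before dosing leaves this at 353.

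**Share of month-only TEAEs lost.** Last dose is at Day 85 and the flag requires onset before last dose plus 35 days, so the window is Days 1-119. The share lost is the proportion of onsets whose 1st-of-month date falls before first dose, averaged over 365 first-dose dates. The documents give no onset distribution, so four are assumed:

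| Assumed onset over the 119 days | Share lost |
|---|---|
| Uniform | 12.4% |
| Exponential, mean 60 days | 24.3% |
| Exponential, mean 30 days | 36.8% |
| Exponential, mean 15 days | 55.8% |

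By period of onset (uniform within the period), the share lost is 86.8% in Days 1-7, 52.3% in Days 1-28 and 0.08% in Days 29-119. The loss is therefore almost entirely in the first four weeks.

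**Events per arm.** Protocol 2.2.1 reports "12 [22.6%] participants with 16 events" on 0.01% ointment in phase 2a, and 26 events on vehicle. Table 1 gives 36 + 17 = 53 active and 34 + 17 = 51 vehicle participants.

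- Active: 16/53 = 0.302 events per participant; x 30 = 9.1 events (lowest arm total).
- Vehicle: 26/51 = 0.510 events per participant; x 40 = 20.4 events (highest arm total).

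The share of AEs with month-only dates is not given; 1% to 10% is assumed. Expected loss = events per arm x share month-only x share lost:

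- Uniform: 9.1 x 1% x 12.4% = 0.01 to 20.4 x 10% x 12.4% = 0.25.
- Mean 30 days: 9.1 x 1% x 36.8% = 0.03 to 20.4 x 10% x 36.8% = 0.75.
- Mean 15 days: 9.1 x 1% x 55.8% = 0.05 to 20.4 x 10% x 55.8% = 1.14.

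The phase 2a observation period was shorter (6 weeks of treatment plus 4-5 weeks of follow-up, 70-77 days). Scaling to 119 days multiplies the uniform case by 119/77 to 119/70 = 1.55 to 1.70, which raises its upper end to about 0.4. The mean-15-day upper end hardly moves (1.14 to 1.15), because nearly all onsets fall inside both periods.

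**The case against.** The strongest reply is that the outcome depends on a document that is not available here. SAP 3.5 and 6.7 place safety endpoints and AE tables under CDISC and CaPS, and the description of the rule as conservative suggests that an inclusive result was intended. This stands in part. A reader might infer that TEAEs will be lost in this trial, and the documents do not establish that. They establish that an explicit study rule lacks a floor and that no text says CaPS overrides or completes it.

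The second reply is that partial dates are least likely where the rule bites. Visits fall at Days 8, 15 and 29, investigators must pursue adequate information on each event (Protocol 8.3.3), and monitors verify CRF data against source (Protocol 10.1.8). This also stands. If no month-only dates arise in Days 1-14, the share lost falls to 4.0% (uniform) or 12.1% (mean 30 days).

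A reader might also infer that the rule favours active treatment. The documents do not support this: the rule is the same in every arm, and nothing is known about the frequency of partial dates by arm. Nor does it touch the efficacy conclusions: "Statistical inference will be made on the primary endpoints: IGA/PGA success rate at Week 12". AE recording, SAE reporting and the separate local tolerability summary (SAP 6.7.5) do not depend on the flag.

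Finally, it might be said that SAP 3.5.1 ignores a Day 1 AE with a missing time. It does not. The time would be set to the earliest possible value; the difficulty is that the inclusion and exclusion sentences then disagree.

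The cost of a floor, that some screening AEs would be counted as TEAEs, is real and is set out under the fix.

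**Conclusion.** The point holds as a defect in the text of SAP 3.5.1, of minor severity. Read literally, the section excludes AEs with ambiguous partial start dates near first dose from a secondary safety endpoint, contrary to its stated intent. That rests on the wording alone.

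The size is uncertain and probably small: about 0.01 to 1.1 events per arm across uniform to early (mean 15 days) onset. This depends on an assumed 1-10% of AEs having month-only dates, on assumed onset distributions, and on phase 2a event rates. Those rates come from 0.01% ointment and vehicle only, so they say nothing about the 0.03% and 0.06% arms. A participant leaves the incidence count only if the lost event was their sole TEAE.

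The Day 1 point applies only if AE clock times are collected, which neither document says.

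**What to change.** In SAP 3.5.1, add:

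- When an AE start date is partial, and neither the known components nor the AE end date show onset before first dose, impute the later of the earliest possible date and the first dose date. Flag the event as a TEAE, subject to the existing upper bound.
- If clock times are collected, treat a Day 1 AE with a missing time as treatment-emergent unless the record shows pre-dose onset, and make the inclusion and exclusion sentences agree on whether they compare dates or dates and times.
- If CaPS already contains this rule, cite it instead.

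The drafting cost is a few sentences, with no change to data collection or to the primary analysis. The statistical cost is that some true screening AEs with partial dates will be counted as TEAEs, in any arm. If their onset is uniform over a 28-day screening period, about 52% of month-only screening AEs share the calendar month of first dose and would be reclassified before the end-date check; that check reduces the figure by an unknown amount. Adding pre-dose events to all arms can slightly dilute a comparison between arms, but it avoids leaving out early on-treatment events.

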#### **3.5.2. Laboratory Data**

The laboratory tests will be performed at time points identified in the Schedule of Activities. Unscheduled clinical labs may be obtained at any time during the study to assess any perceived safety concerns at the investigator's discretion.

### 3.5.3. Vital Sign

Vital signs (blood pressure, pulse, and temperature) will be measured after a minimum of 5 minutes rest as indicated in the SoA.

### 3.5.4. Electrocardiograms

Standard 12-lead ECGs should be collected at times specified in the SoA.

### 3.5.5. Local Skin Tolerability

The investigator or designee will assess tolerability at the site of study intervention application, focusing on the non-lesion skin, immediately post application of the study intervention as indicated in the Schedule of Activities.

## 4. ANALYSIS SETS (POPULATIONS FOR ANALYSIS)

Data for all participants will be assessed to determine if participants meet the criteria for inclusion in each analysis population prior to releasing the database and classifications will be documented per standard operating procedures. For participants with multiple enrollment, only the participant identifier and data under initial enrollment will be included and summarized. Data collected for other enrollments will be included only in listings and narratives. For IGA, PGA, EASI and PASI related endpoints that require qualified raters, evaluations at visits by non-qualified raters will be excluded.

Participant Analysis Set	Description
ITT Analysis Set	All participants randomly assigned to study intervention. Participants will be analyzed according to the randomized intervention.
Safety Analysis Set	All participants randomly assigned to study intervention who took at least 1 dose of study intervention. A randomized but not treated participant will be excluded from the safety analyses. Participants will be analyzed according to the intervention received.

Participant Analysis Set	Description
CCI	

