### **8.1.3. Rater Qualifications**

For specific rating assessments, only qualified raters will be allowed to evaluate and/or rate participants in this study. The minimum qualifications a rater must meet for each study rating assessment will be outlined in the Rater Assessment Guide or Rater Qualification Plan. The level of experience with the target population (or equivalent), specific scale experience (or equivalent), and certification required (if applicable) will be listed and used to determine whether a rater is approved for a given assessment.

**To assure consistency and reduce variability, the same evaluator should assess all dermatological clinical evaluations for any individual participant throughout the study whenever possible.**

- A backup experienced and qualified protocol-trained evaluator will only be allowed and documented in case of emergency or special situations when the designated evaluator is unable to perform the evaluation.
- The rater(s) must become certified to perform selected study assessments before he or she can participate in the conduct of the study.

For specifically defined assessments, rater training and standardization exercises may be conducted, and written documentation will be provided by the site for each rater's certification. In return, each site will be provided written documentation outlining each rater's certification for specific study assessments. Recertification may be required at periodic intervals during the study. The raters who administer specific study assessments will be documented in a centralized location and all site staff who administer ratings will be verified in the site study documentation during the conduct of the study.

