**Table 1. Summary of Major Changes in SAP Amendments**

Version/ Date	Associated Protocol Amendment	Change	Rationale
1/19May2022	Original 21Apr2022	Not Applicable	Not Applicable
2/7Jul2023	Protocol amendment 1 02Nov2022	Section 1 updated protocol version	Protocol amendment
		Section 4. Added handling rules for multiple enrollment	A participant with multiple enrollment was identified
		Section 6.1.2: Clarified intended weight used for stratified analysis is minimum risk weight instead of Mantel- Haenszel weight.	Minimum risk weights are designed to improve precision and reduce bias and can minimize the power loss that can occur when constant odds ratio is not met.
		Section 6.5: Deleted subset analysis for adolescent	There were only few adolescent enrolled for the study.

3	Protocol amendment 1 02Nov2022	Section 4: added statement about excluding evaluation at visits by non-qualified raters	A rater unqualified for PGA/PASI evaluated 10 PsO participants at several visits and such data need to be excluded.
---	-----------------------------------	---	---

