## **5.3. Methods to Manage Missing Data**

### **5.3.1. Efficacy Data**

Analysis of binary data including primary endpoints will use the primary estimand (E1). All missing values, except missing due to COVID-19 pandemic, will be set to a failure ([Section 6.1.1](#)).

Continuous secondary endpoint analysis will use the secondary estimand (E2). For each landmark analysis (e.g., cross sectional analysis by week) missing data, except missing due to COVID-19 pandemic, will be imputed using a control-based imputation method ([Section 6.2.2](#)).

Summaries of tertiary/exploratory continuous data will use the observed data only and no additional considerations are needed.

If a participant misses a visit due to COVID-19, he/she will be excluded from the analysis for that visit; If a participant discontinues treatment or withdraws from the study due to

COVID-19, he/she will be excluded from the analyses after the treatment discontinuation visit or study withdrawal visit, respectively.

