## **6. ANALYSES AND SUMMARIES**

### **6.1. Primary Endpoint(s)**

#### **6.1.1. Main Analysis**

- Estimand strategy: Primary Estimand ([Section 2.2.1](#)). This estimand is intended to provide an estimate of the treatment effect in the absence of prohibited medication use in a population that may or may not be fully compliant with the treatment.
- Analysis set: ITT Analysis Set ([Section 4](#)).

- Analysis methodology: A landmark analysis of the IGA/PGA success endpoints at Week 12 will be performed using the ITT analysis set. The proportions responding and the corresponding risk difference comparing active treatment arm to vehicle group will be analyzed using the unconditional exact method; the risk differences and the corresponding 2 sided unconditional exact 95% confidence intervals will be computed using Chan and Zhang (1999) method. The overall family wise Type I error rate will be controlled at the 1 sided 0.025 level using the Hochberg step up procedure.
- Intercurrent events and missing data: A) Prohibited medication – response will be considered as failure for time points after start date of the event for participants who receive prohibited medication post randomization. B) Withdrawal and all other events, except COVID-19 pandemic, leading to missing data will be treated similarly assuming that participants no longer receive benefit from the study intervention and hence will be considered as failure. C) COVID-19 pandemic: if a participant misses a visit due to COVID-19, he/she will be excluded from the analysis for that visit; If a participant discontinues treatment or withdraws from the study due to COVID-19, he/she will be excluded from the analyses after the treatment discontinuation visit or study withdrawal visit, respectively. D) Inadequate compliance – participants data will be used as recorded.
- Proportions, risk differences and 95% confidence intervals will be presented.

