### **6.2.2. Continuous Secondary Endpoints**

Continuous secondary endpoints include percent CFB in EASI total score, CFB in PASI total score, and percent CFB in affected BSA.

- Estimand strategy: Secondary estimand ([Section 2.2.2](#)). This estimand is intended to provide an estimate of the treatment effect in the absence of prohibited medication use in a population that may or may not be fully compliant with the treatment.
- Analysis set: ITT Analysis Set ([Section 4](#)).
- Analysis methodology: A landmark analysis of these continuous endpoints at Week 12 will be performed by ANCOVA with baseline as a covariate. Missing data, except missing due to COVID-19 pandemic, will be imputed using a control-based imputation method. PROC MI will first be called to impute missing vehicle observations under the assumption data are missing at random (MAR) and impute

missing active treatment observations assuming they are similar to corresponding vehicle arm. The imputation will utilize ANCOVA model including baseline as a covariate fitted using only vehicle arm data. The analysis will combine the results from the multiple imputations using Rubin's rule's as implemented in SAS PROC MIANALYZE. MMRM models may also be used on observed data at all time points as sensitivity analyses. The fixed effects of treatment, visit, and treatment by visit interaction will be included. Baseline value will be included as a covariate. No adjustments for multiplicity will be made.

- Intercurrent events and missing data: A) Prohibited medication: all scores measured at time points after start date of the event for participants who receive prohibited medication post randomization will be excluded from the analysis and treated as missing scores. Missing scores will be imputed. B) Withdrawal and all other events leading to missing data, except COVID-19 pandemic: all missing scores will be imputed. C) COVID-19 pandemic: if a participant misses a visit due to COVID-19, he/she will be excluded from the analysis for that visit; If a participant discontinues treatment or withdraws from the study due to COVID-19, he/she will be excluded from the analyses after the treatment discontinuation visit or study withdrawal visit, respectively. D) Inadequate compliance – participants data will be used as recorded.

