## 9. APPENDICES

### Appendix 1. Summary of Efficacy Analyses

Efficacy Endpoint	Analysis Type	Population	Data Inclusion and Rules for Handling Intercurrent Events and Missing Data	Analysis Model
Week 12 IGA / PGA Response	Primary	ITT	NRI	Chan & Zhang
	Sensitivity	ITT	NRI	Minimum Risk
	Supportive	ITT	NRI	Generalized Linear Mixed Model
	Supportive	ITT	NRI	Bayesian Emax
Week 12 EASI/PASI-75 Response	Secondary	ITT	NRI	Chan & Zhang
Week 12 PCFB in EASI / CFB in PASI	Secondary	ITT	MI	ANCOVA
PCFB in EASI / CFB in PASI	Sensitivity	ITT	OC	MMRM
PP-NRS Rate / IGA of clear or almost clear // PGA of clear or almost clear	Secondary	ITT	NRI	Chan & Zhang
CCI [REDACTED] [REDACTED]	Exploratory	ITT	NRI	Chan & Zhang

PCFB= Percent change from baseline; CFB= Change from baseline; ANCOVA = Analysis of Covariance; NRI = Non-Responder Imputation; OC = Observed Cases.

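### SAP version 3 excludes PGA/PASI ratings by a non-qualified rater without saying how the gap is handled; read literally, an affected Week 12 PGA becomes a treatment failure

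*SAP*

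**What the plan says.** Protocol 8.1.3 sets the standard: "For specific rating assessments, only qualified raters will be allowed to evaluate and/or rate participants in this study". SAP Table 1 records that it was not met: "A rater unqualified for PGA/PASI evaluated 10 PsO participants at several visits and such data need to be excluded". The only change listed for SAP version 3 is in Section 4: "For IGA, PGA, EASI and PASI related endpoints that require qualified raters, evaluations at visits by non-qualified raters will be excluded". Neither place names the visits or arms affected, or says what status an excluded value then has.

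The missing-data text contains no exception for raters:

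- SAP 5.3.1, binary endpoints: "All missing values, except missing due to COVID-19 pandemic, will be set to a failure".
- SAP 6.1.1, event B (also in 2.2.1): "Withdrawal and all other events, except COVID-19 pandemic, leading to missing data will be treated similarly assuming that participants no longer receive benefit", so the value counts as failure.
- SAP 6.1.1, event C, the only exception: "if a participant misses a visit due to COVID-19, he/she will be excluded from the analysis for that visit".
- SAP Appendix 1 ("NRI = Non-Responder Imputation") assigns this rule to all four Week 12 IGA/PGA analyses (primary, minimum risk, generalized linear mixed model, Bayesian Emax) and to EASI/PASI-75.
- SAP 6.2.2, continuous endpoints: the imputation treats "missing active treatment observations assuming they are similar to corresponding vehicle arm".

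The ITT set keeps every randomised participant in the denominator.

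**The concern.** Section 4 removes the rating but not the participant. With nothing further said, the value is missing for a reason other than COVID-19, and the sections above turn it into a failure. Event B rests on the idea that the participant has stopped benefiting. That does not describe someone who attended and was rated, but by the wrong person. A rater's qualification carries no information about response. It is closer to a COVID-19 miss, which the SAP handles by leaving the participant out of that visit.

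Failure scoring takes away more successes where success is common (50% planned on active) than where it is rare (8% planned on vehicle). On average it therefore pulls the primary psoriasis difference towards zero. Appendix 1 lists no PGA-success or PASI-75 analysis under any other rule, so the effect of the choice would not be visible.

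Baseline raises a separate problem. PGA is scheduled at Screening, so SAP 3.4 offers a fallback for a lost Day 1 value. The psoriasis Schedule of Activities (Protocol 1.3.2) first schedules PASI on Day 1. If that rating is excluded, PASI-75 cannot be derived at any visit and is failed throughout, and change in PASI has no starting value.

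**Working it through.** **Inputs.** From SAP 5.1: 30 per arm, 50% versus 8% PGA success (42 points), one-sided 0.008 per dose, unconditional exact test, stated power 92%. From Protocol 4.1: four arms, 1:1:1:1, about 120 participants. From SAP Table 1: 10 participants affected. Assumptions: m of the 10 have no qualified Week 12 PGA in the window (0 to 10), each is equally likely to be in any arm, and being affected is independent of response.

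**Plan's own figure.** Enumerating all outcomes for 30 versus 30, with score ordering and size maximised over the common rate, gives 92.45%. The stated 92% is reproduced.

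**Expected difference under failure scoring.** Each arm loses m/4 of its 30 ratings on average, so each success rate is multiplied by 1 − (m/4)/30 = 1 − m/120, and so is the difference. At m = 10: 50% × 110/120 = 45.8%, 8% × 110/120 = 7.3%, difference 38.5 points. Leaving participants out keeps 42.

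| m | Difference, failure scoring | Difference, left out | Mean power per dose, failure | Mean power per dose, left out |
|---|---|---|---|---|
| 0 | 42.0 | 42.0 | 92.4% | 92.4% |
| 3 | 40.95 | 42.0 | 91.4% | 91.0% |
| 5 | 40.25 | 42.0 | 90.7% | 90.3% |
| 10 | 38.5 | 42.0 | 88.6% | 88.7% |

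**Particular splits** (lost in one active arm / lost in vehicle), failure scoring versus left out:

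- 5/1: (25 × 0.50 − 29 × 0.08)/30 = 33.9 points; power 80.1% versus 89.0%. For a given dose, the chance of at least 5 lost on active with at most 1 on vehicle is 3.9% at m = 10 and 0.1% at m = 5.
- 2/3: (28 × 0.50 − 27 × 0.08)/30 = 39.5 points; 90.6% versus 89.0%.
- 0/5: (30 × 0.50 − 25 × 0.08)/30 = 43.3 points; 95.1% versus 88.2%.

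Uneven splits can therefore move the result either way.

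**Overall error.** Root mean squared error of the active-minus-vehicle difference (squared bias plus variance, averaged over splits), failure versus left out: 10.4 versus 10.5 points (m = 3), 10.5 versus 10.6 (m = 5), 10.8 versus 10.9 (m = 10).

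**PASI-75.** SAP 5.1 plans 50% versus 6%, or 44 points. If m participants lost Day 1 PASI, the same factor gives 44 × (1 − m/120) = 42.9 (m = 3), 42.2 (m = 5) and 40.3 (m = 10).

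**The case against.** The strongest objection is that Section 4 says only that the evaluations are excluded. It does not call them missing or failed. Elsewhere the SAP spells out the consequence: COVID-19 misses are left out of the visit, while scores after prohibited medication are excluded and then treated as missing. Section 4 does neither, so an analyst could read it as leaving the participant out. This stands in part. Failure scoring follows from combining sections and is not stated in Section 4. But two analysts could then reach different primary results, and 5.3.1 as worded favours failure.

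Second, non-responder imputation is a recognised conservative choice, and version 3 was written with the rater problem known. Leaving participants out removes an average bias of at most 3.5 points but does not lower overall error or raise average power. That also stands. The case for change is bias, fit with the estimand's own reasoning, and visibility, not efficiency.

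Third, the documents do not show that Week 12 or Day 1 was affected. Another qualified rating on Days 79 to 99 would also fill the Week 12 window under Appendix 3. Both limits are accepted.

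Fourth, alternatives exist for change in PASI: an optional MMRM on observed data (6.2.2) and descriptive summaries (5.2.2). This is correct, and the gap in planned analyses is confined to PGA success and PASI-75.

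A reader might also infer that failure scoring creates false gaps between doses, which would matter in a dose-ranging trial. The numbers do not support using this as a reason for change. With 30 per arm and two doses both at 50%, a gap of 5 points or more arises by chance about 70% of the time with no rater problem. At m = 10 it is still about 70% under failure scoring and about 73% with participants left out, because denominators shrink.

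**Conclusion.** The point holds as an unspecified consequence with an unsuitable default. The SAP removes a known set of ratings and gives them no handling rule. Its general rules then score an affected Week 12 PGA as failure, and impute an affected PASI change from vehicle data, for a reason unrelated to response.

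The expected loss is 42 × m/120 points from the primary psoriasis difference: none at m = 0, 3.5 points at m = 10. This assumes the planned rates and affected participants spread at random over equal arms. If Week 12 was not affected, the primary result does not change. If Day 1 was also unaffected, the point is minor.

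It would go too far to conclude that the primary result is biased, that power is materially lost, or that dose comparisons are distorted. The affected visits and arms are not given, average power differs by less than half a percentage point between the two treatments of the data, and chance gaps between doses are no rarer under the alternative.

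**What to change.** Before unblinding, state in SAP 5.3.1, 6.1.1, 6.2.2 and Appendix 1, with matching wording in the estimands of 2.2.1 and 2.2.2:

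1. A rater-excluded evaluation with no qualified rating in the visit window is handled like a COVID-19 miss: the participant is left out of that visit's analysis.
2. Participants with no qualified baseline PASI are left out of PASI-based endpoints.
3. Non-responder imputation (control-based imputation for change in PASI) is kept for these cases as a sensitivity analysis. If the sponsor prefers it as the main rule, the left-out analysis becomes the sensitivity analysis.
4. Affected evaluations are counted by arm and visit in the report.

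The cost is a few sentences, one count table and one sensitivity table. The statistical price is slightly smaller denominators, in arms of about 30, and slightly larger variance at affected visits.
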